3.3. SAFETY OBJECTIVES

The safety objectives of this study are to determine the safety and tolerability of 2 doses of ITI-007 adjunctive to treatment with lithium and valproate via:

- Incidence of adverse events (AEs);

- [REDACTED]

• [REDACTED]

• [REDACTED]

[REDACTED]

[REDACTED]

4. STUDY DESIGN

4.1. GENERAL DESCRIPTION

Study participation will last approximately 10-12 weeks (up to 9 visits) and will include the following periods: a *Screening Period*, lasting up to 2 weeks (unless medical monitor approves longer); an *On-Treatment Period* of 6 weeks of daily administration of study medication, and a *Safety Follow-up Period* of approximately 2 weeks after last dose of study medication (or within 1 week of early termination, if possible). The timing and assessments during each study period are described in the Schedule of Events (Table 6-1 of the protocol and Appendix 1 of this SAP).

Approximately 520 patients (173 patients/ treatment group) will be randomized in a 1:1:1 ratio to receive one of three study treatments: 40-mg ITI-007, 60-mg ITI-007, or placebo at approximately 93 global sites. The sample size estimation assumes a common dropout rate of 15% at Day 43, and a common within-patient correlation of 0.7 for the change from baseline in MADRS total scores at Days 8, 15, 22, 29, 36 and 43. This will provide approximately 90% power to detect an effect size of 0.4.

The primary analysis strategy will be based on overall ITT patients and will follow the study protocol.

An alternative analysis strategy specific for Non-US submissions will be considered, details on this approach can be found in Appendix 4 of this SAP.

4.2. [REDACTED]

[REDACTED]

[REDACTED]

[REDACTED]

Sections 7.5.4 and 7.5.6 of the protocol discuss adding the treatment-by-site (or pooled site)

Section 7.5 of the protocol discusses the pooled site algorithm, "If the primary efficacy analysis model presents convergence issues due to the too small number of patients per site, including pooled sites, the same site pooling algorithm will be applied again, but this time pooling sites with fewer than a pre-specified larger number of ITI-007 patients per site within each country or geographic region, as described in the SAP." Since there are efforts using different covariance structures if MMRM failed to converge and the failed to converge issues are often due to subject level data, not site level, the pooling algorithm will be considered final once there are 2 ITT patients per treatment group for each site. Section 7.2 of the protocol specifies the fixed sequence of testing for the primary and key secondary endpoints. The order in this plan has been updated to prioritize the 60 mg vs placebo analyses for the primary and key secondary endpoint first. If both of those endpoints are significant, testing will proceed to the 40 mg vs placebo analyses. More details can be found in section 7.2.

5. PLANNED ANALYSES

5.1. INTERIM ANALYSIS

No interim analyses will be performed.

5.2. FINAL ANALYSIS

The analyses detailed in this SAP will be performed by [REDACTED]
[REDACTED]
[REDACTED]

5.3. [REDACTED]

A blinded sample size re-estimation may be performed when 70% of randomized patients have
[REDACTED]
[REDACTED]
[REDACTED]
[REDACTED]
[REDACTED]

6. ANALYSIS SETS

Analysis of efficacy and safety endpoints will be performed based on the analysis sets defined in this section and as specified for each endpoint throughout this SAP. The inclusion/exclusion of patients from each analysis set will be determined prior to the final analyses (and approved by ITCI) based on blinded data review.

Unless otherwise specified, the ITT Set will be used for efficacy endpoints and the SAF Set will be used for safety endpoints.

6.1. ALL PATIENTS ENROLLED [ENR] SET

The All Patients Enrolled (ENR) Set will contain all patients who provide informed consent for this study.

6.2. ALL PATIENTS RANDOMIZED [RND] SET

The All Patients Randomized (RND) Set will contain all patients who signed informed consent and were randomized to study medication.

For analyses and displays based on RND, patients will be classified according to randomized treatment.

6.3. INTENT-TO-TREAT [ITT] SET

The Intent-to-Treat (ITT) Set will contain all randomly assigned patients who received at least one dose of study medication and who had a valid (pre-dose) baseline measurement and at least one valid post-baseline measurement of rater-administered MADRS total score. All analyses using the ITT Set will classify patients according to randomized treatment, regardless of the treatment received during the course of the study.

6.4. SAFETY ANALYSIS [SAF] SET

The safety analysis (SAF) Set will contain all patients who received at least one dose of study medication. All analyses using the SAF Set will classify patients according to treatment actually received. In case of incorrect dosing, the treatment most often received will be taken as the actual treatment.

[REDACTED]

[REDACTED]

[REDACTED]

[REDACTED]

[REDACTED]

[REDACTED]

7. GENERAL CONSIDERATIONS

Relative Study Day will be calculated from the date of Day 1, which is the day of first treatment with double-blind study medication, and will be used to show the start and/or stop days of treatment, study procedures and assessments, prior, concomitant, and post-treatment medications, and adverse events.

- If the date of the treatment, procedure, or event is on or after Day 1 date then:

Relative Study Day = (date of variable of interest – Day 1 date) + 1.

- If the date of the treatment, procedure, or event is prior to the Day 1 date then:

Relative Study Day = (date of variable of interest – Day 1 date).

If the date of the treatment, assessment, or event is partial or missing, Relative Study Day, and any corresponding event durations will appear missing in the listings.

Analyses presented by visit or study day will be based on the protocol defined scheduled visits including scheduled, unscheduled and early discontinuation visits. Visit windows for unscheduled visits and early discontinuation visits are defined in Table A, which provides the mapping of relative day ranges to the scheduled target days and the study periods. If more than one assessment is available in the same 'Range of Relative Study Days' (window), the assessment closest to the Scheduled Target Day will be selected and assigned to the Scheduled Target Day. If two or more assessments are available in the same window and are equidistant from the Scheduled Target Day, the latest assessment will be selected. The assessment used in the by-visit summary may differ from the assessment to be carried forward for the LOCF methodology, described in Section 7.1, since the latest assessment per visit window will be carried forward for the LOCF analyses.

Listings will include scheduled, unscheduled, retest and early discontinuation data.

Table A: Mapping of Relative Day Ranges to Schedule Target Day

Study Phase	Study Period	Range of Relative Study Days	Scheduled Target Day	Scheduled Study Week
Pre-Treatment	Screening	1-14* days before Day 1 date	Day -14	-2
Pre-Treatment	Baseline	Day 1 date (definition of baseline varies by assessment – see descriptions below)	Day 1	0
Study Treatment	On-Treatment	2 to 11 days relative to Day 1 date	Day 8	1
Study Treatment		12 to 18 days relative to Day 1 date	Day 15	2
Study Treatment		19 to 25 days relative to Day 1 date	Day 22	3
Study Treatment		26 to 32 days relative to Day 1 date	Day 29	4
Study Treatment		33 to 39 days relative to Day 1 date	Day 36	5
Study Treatment		≥40 days relative to Day 1 date and after the last dose of treatment and before the start of the Safety Follow-up Period (one day after actual Day 43 visit)	Day 43	6
Post-treatment	Safety Follow-up	> 43 days relative to Day 1 date for treatment completers (42 day on-treatment) and after Day 43 post-treatment assessments or after early discontinuation visit (for patients who terminated early).	Day 57	8

*Not to exceed 28 days

First treatment with study medication and baseline assessments are scheduled for Visit 2 on Relative Study Day 1. For analysis purposes, baseline is defined as the last non-missing pre-treatment measurement.

Assessments will be considered baseline if the assessment date is before the date of the first treatment of the 6-week On Treatment Period or if the assessment was done on Study Day 1 and, according to the Study Schedule of Events, was supposed to be performed on Day 1, prior to treatment. Rater assessments (MADRS, [REDACTED] CGI-BP-S, [REDACTED] originally scheduled for Day -1 that are rescheduled for Day 1 and are confirmed to have been conducted prior to first dose will be considered baseline.

Unless otherwise specified, the following calculations will be used for change from baseline [REDACTED] of quantitative measurements:

Change from baseline will be calculated as:

- Value at Visit X – Baseline Value

[REDACTED]

[REDACTED] [REDACTED]

All investigative sites with fewer than 2 ITT patients per treatment group will be pooled as follows: The largest site with fewer than 2 ITT patients per treatment group will be pooled with the smallest site with fewer than 2 ITT patients per treatment group within the same country or geographic region. If this results in a pooled site still having fewer than 2 ITT patients per treatment group, this site will be pooled together with the next smallest investigative site within the same country or geographic region, if one exists; otherwise, no further pooling is needed. Sites with the same number of ITT patients will be ordered in ascending order of their numerical site identification number. This will serve as a tie-breaker rule in case multiple sites have the same number of ITT patients. Should the primary efficacy analysis model present convergence issues, after testing the sequence of correlation structures, then the site effect will be reconsidered and may be dropped from the model. These pooled investigative sites, as determined based on the primary efficacy response variable, will be used for any analysis that has investigative site as a fixed effect in the model. The actual investigative site numbers will be included in the listings. For sensitivity analyses where site is a factor, additional pooling will be performed starting from the ITT pooled sites. Sites with patients who are in SEN Set but not ITT will be pooled, using the same algorithm as outlined above.

The default significance level for statistical tests will be 5%; confidence intervals will be 95% and all tests will be two-sided, unless otherwise specified in the description of the analyses. All analyses will be conducted using SAS® version 9.4 or higher.

7.1. MISSING DATA

The total and subscale scores of any assessment with more than one item, such as rater-administered MADRS, will be derived from individual items. Any individual missing item in any scale will not be imputed. If one or more items are missing at a visit, then the associated total

[figure not shown]
score or subscale score will be set to missing. A sensitivity analysis will be explored which imputes the missing MADRS total score when 2 or fewer individual items are missing. Specifically, if there are more than 2 items with missing scores, the MADRS total score will be set to missing; when ≤ 2 items with missing score, the MADRS total score at a particular visit will be derived as follows:

$$\text{MADRS total score} = 10 * (\text{sum of non-missing item scores}) / (\text{number of non-missing items})$$

Change from baseline in the rater-administered MADRS total score will be evaluated for the ITT Set, using the same MMRM method specified for the primary analysis.

The main objective of the analyses of this study is to evaluate the effect of ITI-007 compared to placebo if the treatment is administered for the planned study duration. In order to evaluate this estimand in the presence of patients that may discontinue treatment prematurely, the primary efficacy analyses will be performed based on an assumption of data being missing at random (MAR). This implies that patients discontinuing from treatment early are considered to have unobserved values similar to the observed ones in their treatment group for patients who have similar history, i.e., the distribution of the unobserved future outcomes for patients who had discontinued treatment is the same as the distribution of the observed outcomes for those who continued treatment, conditional on the available data prior to discontinuation.

The Mixed-Effects Model for repeated Measures (MMRM) will be used for the analysis of the primary efficacy endpoint. The MMRM approach does not impute missing data but is based on all patients included in the analysis set using all available longitudinal data (either complete or partial). This approach is based on the MAR assumption as described above.

7.2. MULTIPLE COMPARISONS/ MULTIPLICITY

The study is designed to evaluate the primary and key secondary efficacy endpoints of two doses of ITI-007, 60 mg and 40 mg versus placebo, which involves multiple comparisons. A fixed sequence procedure will be used to control the overall Type I error rate.

The primary and key secondary efficacy endpoints will be tested in the following order:

- 1) ITI-007 60 mg vs placebo comparison change from baseline in MADRS total score at Day 43;
- 2) ITI-007 60 mg vs placebo comparison change from baseline in CGI-BP-S Depression score at Day 43;
- 3) ITI-007 40 mg vs placebo comparison change from baseline in MADRS total score at Day 43;
- 4) ITI-007 40 mg vs placebo comparison change from baseline in CGI-BP-S Depression score at Day 43

All tests will be performed at the 0.05 level. If at any step a hypothesis test does not show statistical significance, then all hypotheses at subsequent steps will not be tested for significance and their p-values will be reported for descriptive purposes only.

There will be no multiplicity adjustments for the comparison of other secondary or exploratory endpoints.

[REDACTED]

[REDACTED]

[REDACTED]

[REDACTED]

[REDACTED]

[REDACTED]

8. OUTPUT PRESENTATIONS

The tables, listings and figures (TLFs) shells provided with this SAP describe the presentations for this study and therefore the format and content of the summary TLFs to be provided by IQVIA Biostatistics.

Continuous variables will be summarized using descriptive statistics (number of patients [n], mean, standard deviation [SD], median, minimum, and maximum, unless otherwise stated). The minimum and maximum will be reported to the same number of decimal places as the raw data recorded in the database. The mean and median will be reported to one more decimal place than the raw data recorded in the database. The SD will be reported to two more decimal places than the raw data recorded in the database.

Categorical variables will be summarized using frequency counts and percentages. Unless otherwise stated, the calculation of percentage will be based on the number of patients in the analysis set of interest.

All p-values will be presented to four decimal places. P-values less than 0.0001 will be presented as "<0.0001".

Confidence intervals (CIs) will be presented to two more decimal places than the raw data.

Source data for summary tables and statistical analyses will be presented as patient data listings.

9. DISPOSITION AND WITHDRAWALS

Patient disposition and withdrawals, will be presented for the ENR Set.

Patient disposition and withdrawals will be presented by treatment group, when applicable, and overall. The number and percentage of patients who were screened, screen failed, randomized, completed or discontinued the 6-week On-Treatment Period, reasons for early

treatment discontinuation, completed or withdrew from the study, and reasons for study withdrawal will be presented. For patients who completed the treatment period, the number who enter safety follow-up will be summarized. [REDACTED]

[REDACTED]

[REDACTED]

[REDACTED]

A patient is defined to have completed the treatment period if the patient has completed the 6-week On-Treatment Period and procedures. Completion of treatment period is recorded on the End of Treatment CRF page.

A patient is defined to have completed the study if the patient has completed the 6-week On-Treatment Period and the End-of-Study assessments on Study Day 57 (± 2). Completion of study is recorded on the Completion/Withdrawal from Study CRF page.

Table B: Reasons for Study Withdrawal and Study Medication Discontinuation Terminology

eCRF Terminology
Adverse event
Death
Lack of efficacy
Lost to follow-up
Protocol violation
Physician decision
Screen Failure
Study terminated by sponsor
Patient withdrew consent:
Personal or family reasons
Refused to provide a reason and refused all End of Study procedures
Self-reported Adverse event

Self-reported Lack of efficacy
Other

Adverse event preferred terms associated with worsening of bipolar depression will be identified by the Medical Monitor review prior to database lock. The number and percentage of randomized patients who discontinued due to an adverse event associated with worsening of bipolar depression will be summarized. The number and percentage of randomized patients discontinued due to an adverse event not associated with worsening of bipolar depression will also be presented.

The time to treatment discontinuation due to any reason, adverse events (broken down by association with worsening of bipolar depression as well), lack of efficacy, withdrawn consent, or due to any other reason of special interest will be evaluated separately using the Kaplan-Meier method. Time to treatment discontinuation will be defined in days for those patients who are randomized and receive at least one dose of study medication but discontinue study medication prior to Day 43 as the date of discontinuation minus date of first dose of study medication plus 1. Patients who complete the On-Treatment Period or who discontinue for a reason other than the one being evaluated will be censored.

The number of patients randomized by site will be summarized by treatment group and overall for all randomized patients.

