7.5.1 Patient Disposition, Analysis of Demographics and Other Baseline Characteristics

Patient disposition will be summarized by treatment group, when applicable, and overall, and by study visit when applicable, including incidence of screening failure and incidence of treatment or study discontinuation and the corresponding reasons. The number and percentage of randomized patients who discontinued due to an AE associated with worsening of bipolar depression will be summarized. Similarly, the number and percentage of randomized patients who discontinued due to an AE not associated with worsening of bipolar depression will also be presented. Time to treatment discontinuation due to all reasons, AEs (all, AEs associated with worsening of bipolar depression, and AEs not associated with worsening of bipolar depression), lack of efficacy, or due to any other reason of special interest will be evaluated separately using the Kaplan-Meier method. The Log-rank test will be used to compare the time to discontinuation between each treatment group and the placebo group.

Demographic and baseline characteristics, including bipolar disorder diagnosis and baseline efficacy measures, will be listed and summarized by treatment group and overall. No inferential statistics will be presented.

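### Reason-specific discontinuation curves censor the competing reasons, so they can overstate, and never understate, the probability of stopping for that reason

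*SAP*

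**What the plan says.** SAP section 9 (Disposition and Withdrawals) defines time to treatment discontinuation for randomized patients who took at least one dose and stopped study medication before Day 43. It lists discontinuation for any reason, for adverse events (also split by association with worsening of bipolar depression), for lack of efficacy and for withdrawn consent, and ends the list with "due to any other reason of special interest will be evaluated separately using the Kaplan-Meier method". The censoring rule follows: "Patients who complete the On-Treatment Period or who discontinue for a reason other than the one being evaluated will be censored".

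Protocol section 7.5.1 plans the same method ("lack of efficacy, or due to any other reason of special interest will be evaluated separately using the Kaplan-Meier method"), as does the synopsis, and adds a test: "The Log-rank test will be used to compare the time to discontinuation between each treatment group and the placebo group". The readable text of SAP section 9 does not repeat the test. No cumulative incidence function or other competing-risks method appears in the readable text of either document.

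The possible reasons are the eCRF terms in "Table B: Reasons for Study Withdrawal and Study Medication Discontinuation Terminology". They include adverse event, death, lack of efficacy, loss to follow-up, protocol violation, physician decision and withdrawn consent.

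SAP section 9 also presents simple counts: "The number and percentage of patients who were screened, screen failed, randomized, completed or discontinued the 6-week On-Treatment Period, reasons for early" treatment discontinuation. It adds the number and percentage of randomized patients who stopped for adverse events associated, and not associated, with worsening of bipolar depression. Protocol section 7.5.1 plans these summaries too.

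**The concern.** Kaplan-Meier handles censoring by assuming that a censored patient has the same future risk of the event as those still under observation. That is reasonable for a patient whose follow-up simply ends. It is not reasonable for a patient who has already stopped study medication for lack of efficacy, whose chance of later stopping it for an adverse event is zero. With such patients censored, one minus Kaplan-Meier describes a hypothetical trial in which the other reasons do not operate, and does so only if the reasons are independent. Independence is doubtful here. Table B appears to file self-reported adverse events and self-reported lack of efficacy under withdrawn consent, and the readable text does not say whether these are reassigned. If they are not, patients leaving for closely related causes are censored in the adverse-event and lack-of-efficacy curves.

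The stake is modest. A reader will naturally take the end of such a curve as the share of patients who stopped for that reason. That reading is biased upward, the reason-specific values can add up to more than all-cause discontinuation, and the same report can carry two different figures for the same thing.

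**Working it through.** The documents state no discontinuation probability by reason, so there is no plan figure to reproduce. The check is of direction, then size.

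**Inputs.** Estimator and censoring rule: SAP section 9. Total dropout: "The sample size estimation assumes a common dropout rate of 15% at Day 43" (SAP section 4.1), taken here as the proportion stopping treatment. Arm size: 173 (same section). The share of dropouts due to one reason is not given; I assume 10% to 70%. Totals of 25% and 35% are also assumptions, used only to show the trend.

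**Direction, without a model.** Let d(t) be the number stopping at time t for the reason evaluated and n(t) the number still on treatment.

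- Cumulative incidence = Σ S(t−) × d(t)/n(t), where S is the proportion still on treatment (all reasons).
- One minus Kaplan-Meier = Σ K(t−) × d(t)/n(t), where K falls only at events of the reason evaluated.

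K is never below S, so one minus Kaplan-Meier is never below the cumulative incidence. It is strictly above once a competing exit precedes an event of that reason. For any-reason discontinuation K equals S and there is no excess.

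**Link to the crude percentages.** If status is known for every treated patient to Day 43, S(t−) = n(t)/N, and the cumulative incidence reduces to Σ d(t)/N. That is the crude percentage with treated patients as the denominator.

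**Size under proportional hazards.** With total F and share s, cumulative incidence = s × F, and one minus Kaplan-Meier = 1 − (1 − F)^s.

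| Total F | Share s | Cumulative incidence | 1 − KM | Excess (points) |
|---|---|---|---|---|
| 15% (planned) | 10% | 1.50% | 1.61% | 0.11 |
| 15% | 20% | 3.00% | 3.20% | 0.20 |
| 15% | one third | 5.00% | 5.27% | 0.27 |
| 15% | 50% | 7.50% | 7.80% | 0.30 |
| 15% | 70% | 10.50% | 10.75% | 0.25 |
| 15% | 100% (any reason) | 15.00% | 15.00% | 0 |
| 25% (assumed) | 10% | 2.50% | 2.84% | 0.34 |
| 25% (assumed) | 50% | 12.50% | 13.40% | 0.90 |
| 35% (assumed) | 10% | 3.50% | 4.22% | 0.72 |
| 35% (assumed) | 50% | 17.50% | 19.38% | 1.88 |

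Three equal reasons at 15% give 3 × 5.27% = 15.8% against a true total of 15.0%.

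**Bounds at 15%.** If every competing exit comes first, one minus Kaplan-Meier = sF/(1 − (1 − s)F). For s = one third this is 5.0/90.0 = 5.56%; for s = 50% it is 7.5/92.5 = 8.11%, an excess of 0.61 points. If every event of the reason comes first, the excess is zero.

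**Simulation.** With 173 patients, 15% dropout and shares of 40, 30, 20 and 10% (1000 runs), mean one minus Kaplan-Meier against the mean crude proportion was 6.31% vs 6.02%, 4.76% vs 4.51%, 3.22% vs 3.03% and 1.55% vs 1.45%. It was never lower in any run. The two were equal in 0% to 8% of runs, depending on the reason, most often for the rarest.

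**The case against.** The strongest reply is that the right number is already planned. The counts and percentages by reason in SAP section 9 and Protocol section 7.5.1 are the Day 43 cumulative incidence apart from the denominator (randomized or treated). This stands, and it limits the problem to the curves. It does not cure them: only the curves show timing, and they can end at a value different from the table beside them.

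Second, the excess is trivial against sampling error. At 5% with 173 patients the standard error is √(0.05 × 0.95/173) = 1.66 points, about six times the 0.27-point excess, which is 0.47 of one patient. This also stands. The excess is, however, one-directional and costs nothing to remove.

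Third, SAP section 8 leaves the format of outputs to shells that are not available, so one minus Kaplan-Meier may never be printed as a percentage. That is fair. The figures above are what the stated estimator returns; a survival-type plot carries the same error with the sign reversed.

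Fourth, censoring other reasons is the standard set-up for comparing cause-specific hazards, so the protocol's log-rank tests are sound. I agree.

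A reader might also infer that these curves are the trial's main tolerability and efficacy-failure displays, or that the comparison between arms is materially distorted. The documents do not support either reading. Discontinuations due to adverse events are also summarized by system organ class and preferred term (Protocol section 7.5.7), and adverse-event incidence comes with relative risks (SAP section 16.1.1). Efficacy rests on the MMRM, and the planned distribution plot counts patients who discontinue as non-responders (SAP section 15.1.3). As to the arms, suppose 15% stop in each, with an assumed 3.0% stopping for adverse events on placebo and 8.0% on active. The curves give 3.20% and 8.30%, a difference of 5.1 points instead of 5.0.

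**Conclusion.** The point holds as a minor one. Under the stated rule, each curve for a specific reason estimates something other than the actual probability of stopping for that reason. The error is never downward, and it is upward whenever a competing exit precedes an event of that reason. It would be too strong to say that every curve is overstated: the any-reason curve is exact, and a specific reason is exact if no competing exit comes before its last event.

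At the planned 15% dropout the excess is about 0.1 to 0.3 points under proportional hazards and about 0.6 points at worst. Since the excess in each arm lies between zero and about 0.6 points, it can shift a between-arm difference by no more than about 0.6 points if both arms stop at 15%. Under proportional hazards it rises to 0.3 to 0.9 points at an assumed 25% and 0.7 to 1.9 points at an assumed 35%. The direction needs no assumption; the sizes rest on the assumed split by reason and on reading the planned dropout rate as treatment discontinuation. This is a disposition summary, and the primary and key secondary tests do not use it.

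**What to change.** Amend the sentence in SAP section 9 so that discontinuation for each specific reason is presented with the cumulative incidence function (Aalen-Johansen), other reasons being treated as competing events. Keep Kaplan-Meier for any-reason discontinuation. Label the protocol's log-rank tests for specific reasons as comparisons of cause-specific hazards. State the denominator, so that the Day 43 end of each curve can be reconciled with the percentage by reason in the disposition table.

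The cost is one SAP sentence and an option in the software already named. Dates and reasons are already collected; sample size, alpha and the testing sequence do not change.
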